10.5.3 Main analyses

16.1.1 Main analysis for Objective 5

- The tumour assessments will be derived according to the IWG treatment response criteria for malignant lymphoma (Cheson et al., 2007), by an Independent Radiology/Clinical Review Committee (IRC). The review process will be defined in the IRC Charter.
- The distribution of TTP will be estimated using the Kaplan-Meier (K-M) method. The median TTP along with 95% confidence intervals will be presented (Brookmeyer and Crowley 1982). 25th and 75th percentiles will be considered as well.
- The TTP probabilities at specific time points (1 month, 3 months, 6 months, 12 months, 18 months, 24 months), and the associate 95% CIs (Greenwood formula) will be summarized.
- TTP events will be described according to the type of events (death due to lymphoma, documented tumour progression).
- A plot of the Kaplan-Meier curve for TTP will be provided.
- No formal hypothesis testing will be conducted.

17.1.1 Analysis for Objective 11

TTP will be compared with TTP of each patient's most recent therapy via tabulating descriptive statistics for TTP of patient's most recent therapy. A graph showing the Kaplan- Meier curve for patients' last prior treatment will be generated for the FAS.

The following therapies will be considered as most recent therapy:

- Last prior systemic anti-DLBCL medication (taken from the eCRF page: Prior Cancer Therapies for DLBCL-Medications)
- ASCT in case the last prior treatment was ASCT (taken from the eCRF page: Prior Cancer Therapies for DLBCL-Autologous Stem Cell Transplants)

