3.2 Secondary Objectives

1. To determine the disease control rate (DCR = CR + PR + SD)
2. To determine the duration of response (DoR)
3. To determine the activity of a combination of LEN with MOR00208 in terms of progression-free survival (PFS)
4. To determine the overall survival (OS)
5. To determine time to progression (TTP)
6. To determine the time to next treatment (TTNT)
7. To determine the safety of LEN combined with MOR00208 assessed according to the frequency and severity of adverse events (AEs)
8. To assess the potential immunogenicity of MOR00208
9. To assess the PK of MOR00208

10. To make a preliminary evaluation of ORR, DCR, DoR, PFS, OS, TTP and TTNT in patients treated with a combination of LEN plus MOR00208 in cohorts with a “low risk”, “low-intermediate”, “high-intermediate” and “high” International Prognostic Index (IPI) (see [Appendix B](#))
11. To compare each patient’s TTP on LEN plus MOR00208 with the TTP of their most recent prior therapy
12. To correlate efficacy parameters with certain biomarkers (e.g., baseline tumour CD19 expression level, peripheral NK cell count, constitutional Fc γ RIIIa and Fc γ RIIa polymorphism status).

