10.6.2.2 Duration of Response (DoR) and Time to Next Treatment (TTNT)

DoR is defined as the time interval between the initial time point of tumour response (CR or PR whichever status is recorded first) and the first date that recurrence of progressive disease is documented. Response duration by the local and central assessment will be tabulated with descriptive statistics.

Disease progression is defined as the first occurrence of progressive disease according to the revised response criteria ([Cheson et al., 2007](#)) as assessed by central radiology / clinical readers.

TTNT is defined as the time from study entry (= first dosing) to the institution of next therapy for any reason including disease progression, treatment toxicity and patient preference. TTNT will be descriptively analysed.

10.6.2.3 Time to Event Variables: Progression-Free Survival (PFS), Overall Survival (OS), and Time to Progression (TTP)

PFS is defined as the time elapsed between study entry (= first dosing) and lymphoma progression or death from any cause, whichever occurs first. Patients not experiencing a lymphoma progression or death from any cause will be censored at the last available tumour assessment. The same holds true for patients who are lost-to-follow-up.

OS is defined as time from study entry (= first dosing) until the date of death from any cause. Patients who are alive but have dropped out early will be censored at the time of the last available study visit assessment.

TTP is defined as the time from study entry (= first dosing) until documented lymphoma progression or death as a result of lymphoma. The events of interest are only disease progression and death from lymphoma. Death from other causes will not be taken into account (will be censored) in the TTP evaluation. Patients not experiencing progressive disease will be censored at the last NHL assessment. Deaths from other causes will be censored at the time of death. Early drop-outs without any documented date of progression will be censored at the time of the last NHL assessment.

Kaplan-Meier methodology will be used to evaluate median survival, presenting corresponding statistical parameters and Kaplan-Meier survival curves. Further analyses concerning influence of IPI and GC/non-GC B-cells will be specified in the SAP.

TTP will be compared to the TTP of the patients' most recent therapy by tabulating descriptive statistics (including 95% confidence limits).

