10. To make a preliminary evaluation of ORR, DCR, DoR, PFS, OS, TTP and TTNT in patients treated with a combination of LEN plus MOR00208 in cohorts with a “low risk”, “low-intermediate risk”, “high-intermediate risk” and “high risk” according to the International Prognostic Index (IPI)	
ORR, DCR, DoR, PFS, OS, TTP, and TTNT stratified by:
 
 four risk categories: “low risk”, “low-intermediate risk”, “high-intermediate risk” and “high risk” 2 risk categories: patients with “low risk” and “low-intermediate risk” vs. patients with “high-intermediate risk” and “high” risk 	See section 10.10
11. To compare each patient’s TTP on LEN plus MOR00208 with the TTP of their most recent prior therapy	TTP in patients treated with LEN plus MOR00208, and TTP in each individual’s most recent prior treatment therapy.	See section 10.11
12. To correlate efficacy parameters with certain	Stratification of efficacy parameter according	See section

STATISTICAL ANALYSIS PLAN

 MorphoSys AG
 MOR208C203

biomarkers (e.g. baseline tumour CD19 expression level, peripheral Natural Killer (NK) cell count, constitutional FcγRIIIa and FcγRIIa polymorphism status)	to the following subgroups: 
 • FcγRIIIa affinity (high affinity: FCGR3A-158V homozygosity vs. low affinity: FCGR3A-158F homozygosity, or FCGR3A-158F/V heterozygosity) • FcγRIIa affinity (high affinity: FCGR2A-131H homozygosity vs. low affinity: FCGR2A-131R homozygosity, or FCGR2A-131H/R heterozygosity) • Cell-of-origin (determined by immunohistochemistry/central pathology: Germinal center B-cell (GCB) vs. non- GCB) • Peripheral NK cell numbers at baseline (< median of NK cell numbers/μl vs. ≥ median of NK cell numbers/μl) 	10.12
---	--	-------

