10.5.4 Sensitivity analyses

18.1.1 Sensitivity analyses for Objective 5

- The analyses will be conducted based on the INV response assessment as entered on the 'Lymphoma Tumour Assessment' eCRF page. The same censoring rules will apply as for the analysis based on IRC assessments.
- Patients lost to follow-up or having an event after more than one missed visit, but having an available death date, will be included in the time-to-event analysis and considered as having a TTP event.

19.1.1 Sensitivity analyses for Objective 11

No sensitivity analyses will be conducted.

10.6 Secondary objective 6

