10.11.2 End point and main analysis

End point analyses are described in detail above in section 10.5.3.

10.12 Secondary objective 12

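### Objective 11 asks for a within-patient TTP comparison, but SAP 10.5.3 plans only group-level summaries, which do not show how many patients did better than on their last therapy

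*SAP*

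**What the plan says.** Protocol 3.2, item 11, sets out to compare each patient's "TTP on LEN plus MOR00208 with the TTP of their most recent prior therapy". SAP 10.5.1 and 10.11.1 repeat this.

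The analysis text is short:

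- SAP section 4, Table 1, names the endpoint as two separate quantities: "TTP in patients treated with LEN plus MOR00208, and TTP in each" individual's most recent prior treatment. It gives no ratio, difference or other paired measure.
- SAP 10.5.3 (sub-item 17.1.1) makes the comparison "via tabulating descriptive statistics for TTP of" the patient's most recent therapy. It adds that a Kaplan-Meier curve for patients' "last prior treatment will be generated for the FAS".
- SAP 10.11.2, the section set aside for Objective 11, only refers back: "End point analyses are described in detail above in section 10.5.3".
- SAP 10.5.4 (sub-item 19.1.1) says of Objective 11: "No sensitivity analyses will be conducted".
- For Objective 5, in the same SAP section: "The distribution of TTP will be estimated using the Kaplan-Meier (K-M) method". That summarises study TTP on its own.
- Protocol 10.6.2.3 also plans a tabulation of descriptive statistics, there with 95% confidence limits, and no paired method.

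The addenda add no paired measure. Addendum 5.0 section 20.3 gives time since progression on the last treatment, and section 20.6.1 gives study TTP in centrally confirmed DLBCL.

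**The concern.** The objective is worded per patient and the analysis is worded per group. One marginal summary of prior TTP beside another of study TTP shows whether the two distributions differ. It does not show how many patients stayed progression-free longer than on their last therapy, which is what the objective asks.

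At stake is a listed secondary objective of a single-arm trial. A table presented as the answer to Objective 11 invites statements about individual patients that it cannot support.

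**Working it through.** No sample size, power or event count is involved, so there is no figure of the plan's own to reproduce. The check has three steps.

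**1. Is a paired measure planned anywhere?** The places listed above, read with the addenda, contain no per-patient ratio or difference, no count of patients doing better, no paired plot and no paired time-to-event method.

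**2. Do the two marginal summaries fix the within-patient result?** Take assumed inputs, not from the documents: uncensored lognormal TTPs, log-SD 1 in both periods, median ratio m (study/prior) and within-patient correlation r of the log times. Then

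P(study TTP > prior TTP) = Φ( ln m / √(2(1 − r)) ).

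For m = 1.5, ln m = 0.405:

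| r | √(2(1 − r)) | z | share with longer study TTP |
|---|---|---|---|
| -0.3 | 1.612 | 0.251 | 59.9% |
| 0 | 1.414 | 0.287 | 61.3% |
| 0.3 | 1.183 | 0.343 | 63.4% |
| 0.6 | 0.894 | 0.453 | 67.5% |
| 0.9 | 0.447 | 0.907 | 81.8% |

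Both marginal distributions are identical in all five rows, so the planned outputs could not tell the rows apart. For m = 1.0, z = 0 and the share is 50% at every r. The loss is therefore real when the medians differ. It is modest (60% to 68%) for correlations up to 0.6 and larger only at high correlation.

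**3. Would a Kaplan-Meier curve of the ratio repair it?** Not as the main result. The ratio is study TTP / prior TTP, and its censoring value is (study censoring time) / prior TTP. Both share the denominator. Patients with long prior TTP tend to have small ratios and are also censored early on the ratio scale, so censoring is informative. In simulations with assumed lognormal TTPs and no treatment effect, ordinary Kaplan-Meier gave P(ratio ≥ 1) of 0.53 to 0.54 at 29% to 30% censoring and 0.56 to 0.59 at 51% to 55% censoring, against a true 0.50. The bias favours the study treatment.

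A ratio threshold above 1 also needs a stated reason. For independent, identically distributed exponential times, P(ratio ≥ 1.33) = 1/(1 + 1.33) = 0.43 with no effect at all.

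**The case against.** The case for leaving the plan alone has several parts.

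- *The SAP follows the protocol, and no formal testing is planned for TTP.* This stands. The gap is a missing paired estimate or display, not a missing p-value. The SAP sentence drops the protocol's confidence limits, but SAP 7.2 gives Kaplan-Meier quartiles with 95% CIs by default.
- *The pairs are not lost.* This stands too. SAP 8.7.4 lists start and progression dates for each prior therapy, and SAP 14.5 promises listings of all collected and derived data. A reader might infer that the plan throws the pairing away; it only fails to summarise it.
- *The marginal outputs are richer than two medians.* Also true. A reader might infer that equal medians are compatible with anywhere from 0% to 100% of patients improving. In an uncensored sample they are not: if every patient improves, every order statistic rises and so does the median, and the reverse holds if every patient does worse. The plan also shows whole distributions.
- *The patient's own history is not the only yardstick.* Protocol 10.8 uses a 20% monotherapy ORR as its benchmark, and no decision rule rests on Objective 11. A reader should not infer that the trial has no other reference.
- *Prior TTP is selected and measured differently, so a paired figure could look more exact than it is.* This is the strongest part. Inclusion criterion 4a requires relapsed and/or refractory disease, so most prior TTPs will be observed progressions. Primary refractory disease is an exclusion (Protocol 5.1.1 and 5.4.2), which removes short first-line TTPs. Prior progression comes from historical eCRF dates, while study TTP uses independent review. But the same selection affects the marginal comparison already planned. It is a reason for a caveat, not for omitting the paired summary.

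**Conclusion.** The point holds in a limited form. Objective 11 is a within-patient comparison, its analysis is group-level, and the two marginal summaries do not determine the share of patients who did better. Under the assumed lognormal model that share can lie between about 60% and 82% at a fixed median ratio of 1.5, while equal medians give 50% throughout. These figures rest on assumed distributions without censoring; they illustrate the gap and do not predict this trial's result.

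The documents do not support a claim that the data are unavailable, that a hypothesis test was owed, or that the primary endpoint is affected. The change is worth making because the objective is prespecified and the necessary dates are already collected.

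**What to change.** 1. **Define prior TTP.** SAP 10.5.2 defines TTP only from first study drug. Use the start date of the most recent therapy to its recorded progression. State one partial-date rule: SAP Table 5 imputes a missing progression day to the first of the month, Tables 7 and 9 to the last, and none is assigned to prior TTP. State which start date applies when the most recent therapy is ASCT, since SAP 10.5.3 takes ASCT as a therapy in its own right while Protocol 6.7 counts induction through maintenance as one line. Show patients without a usable prior TTP in their own row.

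2. **Add one table and one paired plot for the FAS.** Give the number and percentage of patients whose study TTP exceeds their own prior TTP, with a 95% CI (Clopper-Pearson, as SAP 9.2 already uses for ORR). Count a patient censored after passing prior TTP as longer, and one censored before reaching it as indeterminate. Report the percentage twice: indeterminate patients all as not longer, then all as longer.

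3. **Do not make an ordinary Kaplan-Meier estimate of the ratio the main result.** Any ratio threshold should be pre-stated and justified by the sponsor; the documents contain none.

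4. **Add a table note** that prior TTP is selected (mostly observed progressions, primary refractory disease excluded, historical eCRF dates rather than independent review), so the comparison is descriptive only.

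The cost is a short derivation, one table and one figure, with no new data collection. The downside is that the gap between the two percentages equals the share of indeterminate patients, so it will be wide if many are censored early. If the sponsor wants only a group-level description, the alternative is to reword Objective 11 to say so.

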10.5.4 Sensitivity analyses

18.1.1 Sensitivity analyses for Objective 5

- The analyses will be conducted based on the INV response assessment as entered on the 'Lymphoma Tumour Assessment' eCRF page. The same censoring rules will apply as for the analysis based on IRC assessments.
- Patients lost to follow-up or having an event after more than one missed visit, but having an available death date, will be included in the time-to-event analysis and considered as having a TTP event.

19.1.1 Sensitivity analyses for Objective 11

No sensitivity analyses will be conducted.

10.6 Secondary objective 6

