10.2.6 Sensitivity analyses

- The main analysis as described in Section 10.2.5 will be conducted on the PPS.
- The main analysis as described in Section 10.2.5 will be conducted based on the INV response assessment as entered on the 'Lymphoma Tumour Assessment' eCRF page. The same censoring rules will apply as for the analysis based on the IRC assessment. If the response assessment is not based on radiological examination the date when the diagnosis of relapse or progression was made by the investigator is considered as the date of progression. The analysis will be conducted using both the FAS and the PPS.
- Patients having more than one missed visit, but having an available death date, will be included in the time-to-event analysis and considered as having a PFS event. The analysis will be performed on the FAS for both IRC and INV response assessment.

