10.5.2 Endpoint: Time to progression

TTP is defined as the time from the first administration of any study drug until documented DLBCL progression or death as a result of lymphoma. Death from other causes than lymphoma will not be considered in relation to the TTP evaluation.

If a patient does not have an event, TTP will be censored on the date of the last tumour assessment before the data analysis cut-off date or the anti-neoplastic therapy start date if the patient started any new anti-neoplastic therapy or the date of death for death from other causes than lymphoma.

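### The TTP sensitivity analysis sets no cause-of-death condition, so an other-cause death after loss to follow-up counts as a TTP event although the endpoint definition censors it

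*SAP*

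**What the plan says.** SAP 10.5.2 runs TTP from first study drug "until documented DLBCL progression or death as a result of lymphoma". It adds: "Death from other causes than lymphoma will not be considered in relation to the TTP evaluation". Its list of censoring dates ends with "or the date of death for death from other causes than lymphoma". Protocol 10.6.2.3 agrees: "Deaths from other causes will be censored at the time of death". For the main analysis, SAP 10.5.3 says "TTP events will be described according to the type of events (death due to lymphoma, documented tumour progression", and names no third type.

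SAP 10.5.4 then gives two sensitivity analyses for Objective 5. The first uses the investigator assessment. The second concerns patients who were lost to follow-up or whose event came after they had missed more than one visit. Any such patient "having an available death date, will be included in the time-to-event analysis and considered as having a TTP event".

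The PFS counterpart in SAP 10.2.6 concerns patients with more than one missed visit and ends in nearly the same words: "having an available death date, will be included in the time-to-event analysis and considered as having a PFS event". PFS counts death from any cause (SAP 10.2.2), so that rule agrees with its endpoint.

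**The concern.** A sensitivity analysis is easiest to interpret when it changes one assumption. This one changes how patients with incomplete follow-up are handled and, for some of them, also what counts as an event. If its result differs from the main TTP analysis, the reader cannot tell which change is responsible.

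The result would not be PFS either. A patient who attends all visits and dies of another cause stays censored under 10.5.2. A patient with the same cause of death who was lost to follow-up becomes an event. Attendance, not the disease, then decides the classification. Other-cause deaths are plausible in this population, because eligibility covers patients unsuited to transplant through advanced age or comorbidity.

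**Working it through.** The documents state no TTP figure (no event count, assumed median or power), so there is nothing to reproduce. The check compares the texts and then gives an illustration.

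**Comparison by type of patient.** The bullet gives no event date; the date of death is assumed.

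| Patient who dies without documented progression | SAP 10.5.2 | SAP 10.5.4, second bullet |
|---|---|---|
| Lymphoma death, visits attended | Event | Event (not touched) |
| Other-cause death, visits attended | Censored at death | Censored at death (not touched) |
| Lymphoma death after loss to follow-up | Event; no exception stated | Event |
| Other-cause death after loss to follow-up | Censored at death | Event |
| Other-cause death after more than one missed visit | Censored at death | Event on the literal reading; not an event if the word means a TTP event |

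Three things follow.

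1. The fourth row is a direct contradiction. The fifth depends on the reading. Neither kind of death fits either of the two event types in 10.5.3.
2. The direction is fixed. With the date of death as end time under both rules, only the status changes, from censored to event. That can lower a Kaplan-Meier curve but not raise it.
3. The third row shows a gap. Under 10.5.2 a lymphoma death is already an event. The rules for loss to follow-up and missed assessments (Tables 13 and 14) are set out for PFS in 10.2.4 and invoked for DoR in 10.3.3, but not for TTP. Protocol 10.6.2.3 censors early drop-outs without documented progression at their last assessment, but does not say what happens if such a patient later dies of lymphoma. The main rule that the bullet is meant to relax is therefore not stated.

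**Illustration (all inputs assumed).** Use independent constant hazards.

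- L = ln 2 / (median TTP) is the hazard of progression or lymphoma death.
- O = −ln(1 − r)/24 is the monthly hazard of other-cause death, where r is its 24-month risk.
- f is the share of other-cause deaths that the bullet captures.
- Median under the bullet = ln 2 / (L + f·O).

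Example with median 12 months, r = 10%, f = 50%: L = 0.6931/12 = 0.05776; O = 0.10536/24 = 0.00439; median = 0.6931/(0.05776 + 0.00220) = 11.56 months.

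Median TTP in months under the bullet, against 12.0 under the definition:

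| r | f = 25% | f = 50% | f = 100% |
|---|---|---|---|
| 5% | 11.89 | 11.78 | 11.57 |
| 10% | 11.78 | 11.56 | 11.15 |
| 20% | 11.54 | 11.11 | 10.34 |

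Over this grid the 24-month rate moves from 25.0% to between 24.7% and 20.0%. If the median may be 8 to 16 months, the fall in the median runs from 0.05 months (8 to 7.95) to 2.83 months (16 to 13.17). The expected number of patients in 80 who die of another cause before any TTP event by 24 months runs from 1.7 to 10.1. Only the share f of these would be affected.

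**The case against.** **Missed-visit branch.** The bullet speaks of patients having an event after more than one missed visit, and 10.5.2 defines what an event is in the TTP section. On that reading an other-cause death never enters this branch. A reader might infer that every death after missed visits is counted; the text does not establish that. The objection stands for this branch. It does not help the other one, where loss to follow-up and a death date are enough.

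**Deliberate worst case.** One could assume that a patient with unobserved disease status who then dies had progressed. That would be legitimate if labelled, but the SAP does not label it and gives no purpose for the analysis. Death from any cause is already covered by PFS and its sensitivity analyses.

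**An emptied analysis.** Restricting the bullet to lymphoma deaths would reproduce 10.5.2 as written. This is correct, so the remedy has to go beyond the bullet.

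**Carry-over from PFS.** The near-identical wording suggests it, but 10.5.4 adds patients lost to follow-up, whom 10.2.6 does not mention. The drafting history is a guess, and the point does not need it.

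**Consequence.** No hypothesis is tested, Objective 11 has no sensitivity analysis, and the primary ORR is untouched. The rule cannot make the treatment look better. All of this stands.

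**Conclusion.** The inconsistency is real but minor. Followed as written, SAP 10.5.4 turns other-cause deaths after loss to follow-up into TTP events, against SAP 10.5.2 and the protocol. On the literal reading it does the same for other-cause deaths after more than one missed visit.

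The direction is certain if death is dated the same way under both rules: the curve can only fall. The size is unknown. A reader might take the illustrated counts or shifts as estimates for this trial. They are not, because they rest wholly on assumed risks and shares, and the true number of affected deaths could be zero. Nor do the documents support a wider conclusion that the main TTP result or any other endpoint is distorted. The effect is confined to one descriptive sensitivity analysis of one secondary endpoint.

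**What to change.** 1. In the second bullet of SAP 10.5.4, count only patients with an available date of death as a result of lymphoma, classified by the rules in 10.7.3.1.6 and 17.6. Keep other-cause deaths censored at the date of death.
2. State how deaths placed in the Unknown category of 17.6 are treated. Counting them as events, labelled as a conservative choice, is one option. Cause is assigned by searching free text, and deaths after loss to follow-up are where it may well be missing.
3. In 10.5.2, state whether the loss-to-follow-up and missed-assessment censoring of Tables 13 and 14 applies to the main TTP analysis. If it does, the sensitivity analysis should differ only in relaxing that censoring. If it does not, the restricted bullet adds nothing except the handling of unknown causes and could be dropped.

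The cost is a few words in one bullet and two or three sentences elsewhere. No new data are needed, since deaths are already classified by relation to progression.
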